## 6.1.2 ADMINISTRATION AND/OR DOSING

As described in Table 1, the patient intervention will be delivered during a routine oncology visit or at home through MyChart. It is expected to take ~15-20 minutes. Provider intervention content will be delivered at an existing lung cancer meeting or online through REDCap. It is expected to take ~15-20 minutes. Patients will be considered to have received a full dose of the intervention if they watch the video and complete the PC needs assessment in the web-based mPal tool. Providers will be considered to have received a full dose of the intervention if they watch the recorded presentation or attend it live.

## 6.2 FIDELITY

### 6.2.1 INTERVENTIONIST TRAINING AND TRACKING

Because the primary component of this intervention is a web-based multicomponent tool, interventionist training and fidelity monitoring procedures are minimal. [name] (PI) and the study team will conduct an in-person training with review of procedures and role plays. [name] or another study team member will observe the first 2-3 patient intervention sessions in clinic and additional sessions as needed. The study coordinator who meets patients in clinic to show them the mPal tool will attend weekly team meetings to receive supervision.

## 6.3 MEASURES TO MINIMIZE BIAS: RANDOMIZATION AND BLINDING

This is a randomized controlled trial design (patient-level randomization). Study staff and patients will not be blinded to allocation; however, study staff and patients will not know allocation until after a patient has completed the baseline questionnaire. The statistician will generate the randomization table, which will be implemented through REDCap.

#### 6.4 CONCOMITANT THERAPY

Patients will be able to receive concomitant treatment while on study. This may include counseling, complementary and alternative therapies, psychotropic medications, and rehabilitation. Indeed, one of the anticipated effects of the intervention is a facilitated referral to supportive services, including palliative care. We will track concomitant treatment use through review of electronic health record for services used during the study intervention period as well as by asking patients at follow-up whether they engaged services while completing the intervention.

### 7 STUDY CONTROL CONDITION

#### 7.1 CONTROL CONDITION DESCRIPTION

Only the patient level component of mPal is randomized. Patients not randomized to the mPal patient implementation strategies will receive usual care.

### 8 STUDY INTERVENTION DISCONTINUATION AND PARTICIPANT DISCONTINUATION/WITHDRAWAL

#### 8.1 DISCONTINUATION OF STUDY INTERVENTION

If a patient or provider discontinues the intervention, but not the study, remaining study procedures will be completed (e.g., post-assessment). Patients and providers who discontinue the intervention will be asked to indicate the reason why they are discontinuing (e.g., intervention burden,; see withdrawal form). If a participant's post-assessment is due to be completed within 2 weeks of discontinuing the intervention, the post will be administered at the time of discontinuation. If the post assessment is scheduled for more than 2 weeks from the date they discontinue the intervention, the post assessment will be administered at the originally scheduled assessment.

Patients may be discontinued from the intervention by the investigative team if the study team or treating physician has concerns about the patient's mental status or psychological wellbeing, at which point procedures for managing patient safety and evaluating adverse events will be followed. The study will document reasons for discontinuing a patient.

## 8.2 PARTICIPANT DISCONTINUATION/WITHDRAWAL FROM THE STUDY

Participants are free to withdraw from participation in the study at any time upon request.

An investigator may discontinue a participant from the study for the following reasons:

- Significant study intervention non-compliance
- Lost-to-follow up; unable to contact subject (see Section 8.3, Lost to Follow-Up)
- Any event or medical condition or situation occurs such that continued collection of follow-up study data would not be in the best interest of the participant (Note: Patients who become hospitalized will still have option to continue the study to complete assessments).
- The patient meets an exclusion criterion (either newly developed [e.g., change in mental status] or not previously recognized) that precludes further study participation.

The reason for participant discontinuation or withdrawal from the study will be recorded.

Patients who sign the informed consent form but do not receive the study intervention may be replaced. Patients who sign the informed consent form and receive the study intervention and subsequently withdraw, or are discontinued from the study, will not be replaced.

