#### 4.4 END-OF-STUDY DEFINITION

A patient is considered to have completed the study if he or she has completed the baseline assessment and the follow-up (T2) assessment. A provider is considered to have completed the study if they complete the baseline assessment and the follow-up (T3) assessment. The end of the study is defined as completion of the follow-up (T2 for patients; T3 for providers) and completion of EHR extraction for follow-up outcomes..

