### 10.2 SAMPLE SIZE DETERMINATION

The sample size of 80 patients is based on the goal of estimating the probabilities and means for 2 feasibility outcome measures (enrollment  $\geq 60\%$  [primary],  retention  $\geq 60\%$ ). We will use feasibility outcomes to inform a future trial. For structured interviews, we anticipate we will be able to identify key themes with 20 interviews.

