#### 10.4.2 ANALYSIS OF THE PRIMARY ENDPOINT(S)

The primary outcome of the feasibility is enrollment ( $\geq 60\%$ ). A one-sample binomial test will be used to compare the observed enrollment percentage to 60%.

Enrollment (primary): Number of patients enrolled divided by the number of eligible patients approached

Retention: The percentage of patients and providers who complete baseline and follow-up questionnaires.

Acceptability: Mean post-treatment patient and provider ratings  $\geq 3.5/5$  on intervention acceptability, feasibility, and appropriateness (psychometrically validated measure; Table 2), and a brief semi-structured interview to explore factors associated with acceptability.

---

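### Section 8.2 allows removal from the study for intervention non-compliance, a ground that among randomized patients only the mPal arm can meet; its relation to Section 8.1 and its handling in the analysis are not stated

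*Combined protocol and SAP*

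**What the plan says.** Section 8.1 covers people who stop the intervention: "If a patient or provider discontinues the intervention, but not the study, remaining study procedures will be completed (e.g., post-assessment"). Section 8.2 covers removal from the study: "An investigator may discontinue a participant from the study for the following reasons", and the first reason listed is "Significant study intervention non-compliance". Neither section says which one governs a patient who is reachable and willing but does not use mPal.

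No threshold for non-compliance is given. The nearest text is in Section 6.1.2: "Patients will be considered to have received a full dose of the intervention if they watch the video and complete the PC needs assessment". For the control arm, Section 7.1 states: "Patients not randomized to the mPal patient implementation strategies will receive usual care". Section 6.3 says that study staff and patients are not blinded, and that allocation becomes known once the baseline questionnaire is done.

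The measures that depend on follow-up are these:
- Section 10.4.2: "Retention: The percentage of patients and providers who complete baseline and follow-up questionnaires". Section 10.2 sets the target at 60% or more.
- Section 4.4: "A patient is considered to have completed the study if he or she has completed the baseline assessment and the follow-up (T2) assessment".
- Section 10.4.3 compares pre-post change between arms with t-tests.

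Section 8.2 also allows replacement of consented patients who never received the intervention, but not of those who received it and later left. Section 10.3 names the sample as 40 plus 40. Sections 10.3 and 10.4 give no rule for analysing patients by assigned arm, no handling of removed patients and no missing-data method.

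**The concern.** Failure to use mPal is one of the things a feasibility pilot is meant to observe. The other Section 8.2 grounds concern loss of contact, the participant's interest, or an exclusion criterion. This one can end follow-up for a patient who could still be reached and would still answer, only because the tool under test was not used.

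The ground applies after randomization, can arise in only one randomized arm, depends on engagement, and is applied at discretion by people who know the allocation. If it is used, the mPal patients with T2 scores are a more engaged subset, compared with a control group that was not filtered in this way. Retention can also change according to which section staff follow. In addition, the equity outcome in Table 2 is meant to describe mPal patients who do not seek referral or do not gain knowledge, and these are the patients whose data would tend to be lost.

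**Working it through.** The only stated figure is the sample size of 80. Section 10.2 gives it without power, standard deviation, dropout or target interval width, so there is no calculation to reproduce. For scale, the exact 95% interval for 48/80 (60%) is 48.4% to 70.8%.

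**Inputs from the documents.** 40 patients per arm and 80 in total (10.2, 10.3); retention target 60%, which is 48/80 (10.2); follow-up read as T2 (4.4). Section 10.4.2 also counts providers; the figures below are for patients.

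**Assumptions.** The documents give no completion, non-compliance, removal or referral rates. All such rates below are illustrative. I read discontinuation from the study as meaning that T2 is not collected.

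**1. Retention with all randomized patients in the denominator.** Let c patients per arm be would-be T2 completers, and let k of them be removed from mPal. Overall retention is (2c − k)/80 and mPal retention is (c − k)/40. Each removal costs 1/80 = 1.25 points overall and 1/40 = 2.5 points in mPal, with no matching loss in control.

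| c per arm | k = 0 | k = 4 | k = 6 | k = 8 |
|---|---|---|---|---|
| 26 | 65.0% | 60.0% | 57.5% | 55.0% |
| 28 | 70.0% | 65.0% | 62.5% | 60.0% |
| 32 | 80.0% | 75.0% | 72.5% | 70.0% |

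Only the first row crosses below 60%. At c = 26 and k = 6, mPal retention is 20/40 = 50% against 65% in control.

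Removed patients may be poor completers anyway. If 8 are removed and each would have completed with probability p, retention is (52 − 8p)/80:
- p = 0.40: 61.0%
- p = 0.65: 58.5%
- p = 1: 55.0%

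It falls below 60% only if p exceeds 0.50.

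**2. Chance of meeting the target.** Sum two independent binomials of size 40, with completion π in control and π(1 − r) in mPal, where r is the fraction of mPal completers removed. The probability of at least 48/80 is:

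| π | r = 0 | r = 10% | r = 20% |
|---|---|---|---|
| 65% | 0.854 | 0.672 | 0.439 |
| 70% | 0.979 | 0.911 | 0.753 |

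**3. Retention if removed patients leave the denominator.** With 26/40 would-be completers in mPal and 8 excluded, mPal retention is (26 − 8p)/(40 − 8). That is 26/32 = 81.3% at p = 0, 20.8/32 = 65.0% at p = 0.65, and 18/32 = 56.3% at p = 1. So retention rises if those excluded were less likely than average to complete. The sign depends on a denominator that the plan does not state.

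**4. Comparison of pre-post change.** Suppose a fraction f of mPal patients gain no more than controls and the rest gain d more. Keeping everyone gives (1 − f)d; removing that fraction gives d. The relative inflation is 1/(1 − f) − 1, which is 5.3%, 11.1% and 25.0% for f = 5%, 10% and 20%.

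If there is no true effect and the removed patients change by 0.5 SD less than those who stay, the false difference is 0.5f SD: 0.05 SD at f = 10% and 0.10 SD at f = 20%. The standard error of the difference is √(2/40) = 0.22 SD with 40 per arm and √(2/28) = 0.27 SD with 28 per arm. The bias is small against that noise, but it is systematic.

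**5. EHR referral, only if removed patients leave the denominator.** The proportion rises by (fraction removed) × (referral among users − referral among non-users). With 8 of 40 removed and rates of 35% and 10%, the full-arm value is (32 × 0.35 + 8 × 0.10)/40 = 30%, against 35% after removal. With 4 to 12 removed and gaps of 15 to 25 points, the rise is 0.1 × 15 = 1.5 to 0.3 × 25 = 7.5 points. If extraction continues for everyone, the rise is zero.

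**The case against.** A reader might infer that the two sections contradict each other outright. They do not. Section 8.1 is limited to people who leave the intervention but not the study, so someone removed under 8.2 is outside it by its own terms. Section 8.2 is permissive and limited to significant non-compliance. What stands is that a patient who ignores mPal can be sent down either path at an investigator's discretion.

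A reader might also infer that the results are distorted, or that mPal retention must fall. The documents support neither. They give no removal rate and no sign of routine use, and a full dose is a 15-20 minute task. The replacement rule could push retention up. Crossing 60% needs completion near the threshold and removed patients who would mostly have completed.

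Nor does the text show that referral is inflated. Table 2 gives referral an EHR source at 3 months, and the release in Section 9.1 covers referral data for up to 12 months post-enrollment. The plan does not say whether extraction continues after removal.

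The plan also has partial safeguards. Reasons for removal are recorded, and Section 10.4.1 compares patients who drop out or do not adhere, which suggests that non-adherent patients are not dropped automatically. But that comparison is descriptive and does not correct a biased arm comparison. Finally, the effectiveness analyses are exploratory and enrollment is untouched. This limits the importance of the point without removing it. Providers could also meet the ground, but they are not randomized, so the imbalance between arms concerns patients only.

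**Conclusion.** The point holds as an unreconciled overlap that permits selective, post-randomization loss of T2 data from one arm. The wording and the one-arm exposure are certain from the text. The consequences are conditional: they arise only if the power is used.

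The comparison of change would then probably favour mPal, on the assumption that disengaged patients gain less. In the illustrations the inflation is 5% to 25%, or 0.05 to 0.10 SD under no effect. Retention loses 1.25 points overall per would-be completer removed if the denominator stays at 80, but can move either way if it does not. The actual size cannot be derived from the documents. This should be corrected before follow-up data are lost; it does not threaten the primary endpoint.

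**What to change.** - In Section 8.2, delete intervention non-compliance from the reasons for discontinuing a participant from the study.
- State that non-compliance is recorded as intervention discontinuation under Section 8.1, with T2 and EHR extraction continuing unless the patient withdraws.
- In Sections 10.3 and 10.4, state that patients are analysed in the arm to which they were assigned and that the patient retention denominator is all randomized patients, including any who are replaced.

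This changes data collection and analysis only. Voluntary withdrawal, the participant-interest ground and the safety procedures stay as written. The cost is a few lines of text and continued T2 attempts for a small number of disengaged mPal patients. Observed mPal effects may look slightly less favourable as a result.

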### 5.5 SCREEN FAILURES

Screen failures will be defined as patients who consent to participate in this study but are not subsequently assigned to the study intervention due to ineligibility or are assigned to intervention, but do not meet eligibility criteria and are withdrawn by investigators. Patients who do not meet the criteria for participation in this trial because of meeting one or more exclusion criteria that are likely to change over time may be rescreened. Examples include improvement in functional status and a progression of disease or disease recurrence for which a patient will begin treatment for advanced stage disease. Rescreened participants will be assigned the same participant number as for the initial screening.

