## 9 STUDY ASSESSMENTS AND PROCEDURES

## 9.1 ENDPOINT AND OTHER NON-SAFETY ASSESSMENTS

**Screening.** We will build a master list form in REDCap linking patient names, MRNs, and study IDs. We will build a separate REDCap form for screening. The eligibility screening form will include patient screener ID, date screened, date must be enrolled by (21 day window), eligibility criteria (e.g., performance status, time on cancer treatment, age, etc.), whether the patient is being rescreened for eligibility, and, if rescreened, the last date of screening. If deemed potentially eligible, additional fields will appear in the eligibility database for tracking dates of upcoming appointments and contact with patients. Patients must be enrolled within 21 days of screening or else they will need to be rescreened.

**Administration of Questionnaires.** Patient-reported measures related to a future efficacy trial and of treatment processes were chosen based on their validity and sensitivity to change in cancer patients and recommendation for clinical trials. These measures will be completed by patients pre-intervention (TP0), ~4 weeks after baseline (T1), and post-intervention (~8-weeks after T0; TP2) on paper, online (REDCap), or by phone. For patients who use MyChart®, a link to the REDCap survey will be provided through a study research message delivered in MyChart®. Patients will use a participation ID on their questionnaires. If more than 30 days pass between baseline and participant viewing the mPal tool, key sections (e.g., palliative care knowledge, palliative care use) of the baseline questionnaire will be re-administered prior to viewing mPal. See **Table 2** for a list of measures to be administered, psychometric properties, assessment schedule, and role in analysis plan. All patient-reported measures will be entered in REDCap in the REDCap project built for those patients who enroll.

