## 12 SUPPORTING DOCUMENTATION AND OPERATIONAL CONSIDERATIONS

## 12.1 REGULATORY, ETHICAL, AND STUDY OVERSIGHT CONSIDERATIONS

### 12.1.1 INFORMED CONSENT PROCESS

#### 12.1.1.1 CONSENT

For patients, written documentation of informed consent will be required prior to completing the baseline assessment and randomization. The consent form will describe the intervention, randomization, study procedures, including audiorecording of the semi-structured interviews, risks, and potential benefits.

For providers, a study cover letter will be required prior to baseline assessment. The cover letter will describe the intervention, study procedures, including audiorecording of the semi-structured interview, risks, and potential benefits.

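### Replacement in Section 8.2 turns on receipt of mPal rather than randomisation, and no rule keeps replaced randomised patients in the retention denominator or their assigned arm (minor)

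*Combined protocol and SAP*

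**What the plan says.** Section 8.2 has two replacement sentences. The first reads: "Patients who sign the informed consent form but do not receive the study intervention may be replaced". The second says that patients who consent and "receive the study intervention and subsequently withdraw, or are discontinued from the study, will not be replaced". Neither mentions randomisation. The same section lists "Significant study intervention non-compliance" among the reasons for discontinuing a participant and does not define it.

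The order of events comes from other sections:
- Section 12.1.1.1: for patients, "written documentation of informed consent will be required prior to completing the baseline assessment and randomization".
- Section 6.3: "study staff and patients will not know allocation until after a patient has completed the baseline questionnaire"; neither group is blinded afterwards.
- Section 9.1 provides for late viewing: "If more than 30 days pass between baseline and participant viewing the mPal tool", key parts of the baseline questionnaire are repeated.
- Section 7.1: "Patients not randomized to the mPal patient implementation strategies will receive usual care".

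Section 5.5 includes among screen failures some patients who are "assigned to intervention, but do not meet eligibility criteria and are withdrawn by investigators".

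On analysis, Section 10.3 gives the patient sample as 40 mPal and 40 usual care. Section 10.4.2 defines retention as the percentage completing baseline and follow-up questionnaires, without saying of whom. Section 10.2 names enrolment and retention, each with a 60% target, as the two measures behind the sample size of 80.

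**The concern.** A patient can consent, complete baseline, be randomised to mPal, learn the allocation, and then be lost before viewing the tool. Under Section 8.2 that patient may be replaced. If the replacement fills one of the 40 mPal places in Section 10.3, the analysis set can consist of 80 patients from which early mPal losses have been removed.

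Two results are exposed. Retention would be overstated, because the removed patients are the ones least likely to return a follow-up questionnaire. The arms would also cease to be comparable as randomised: the mPal arm would be selected for having viewed the tool, while usual care has no matching selection step. The retention estimate is meant to inform a future trial (Section 10.2), so an optimistic figure would carry into its planning.

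**Working it through.** **Does the rule reach randomised patients?** The sequence is consent, baseline, randomisation and disclosure of allocation, then viewing of mPal, which Section 9.1 allows for at more than 30 days after baseline. Section 8.2 applies to anyone who has consented and not received the intervention. That interval includes the time after randomisation, and no section cuts it off there.

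**Does another section settle the analysis?**
- Section 8.1 keeps collecting assessments from patients who stop the intervention but stay in the study. It does not cover patients who leave the study.
- Section 10.4.1 compares dropouts and non-adherers by characteristics. It sets no denominator and no analysis arm.
- Section 10.3 states numbers per arm, with no rule that patients are analysed as randomised.

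**The plan's own figure.** Section 10.2 gives no precision or power target, so 80 cannot be derived from it. For scale, at 60% retention the normal half-width is 1.96 × √(0.6 × 0.4 / 80) = 10.7 percentage points, and the exact 95% interval for 48/80 is 48.4% to 70.8%.

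**Retention with and without replaced patients.** Let C be completers among the 80 counted patients, r the randomised patients replaced, and k the number of those r who complete T2. Follow-up is taken as T2, as in Section 4.4. The documents give none of these counts, so all are assumptions.
- Replaced patients left out: C / 80.
- All randomised patients kept: (C + k) / (80 + r).

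With k = 0:
- C = 48: 48/80 = 60.0%; 48/81 = 59.3%; 48/84 = 57.1%. At r = 4 the overstatement is 60.0 − 57.1 = 2.9 points.
- C = 52: 52/80 = 65.0%; 52/84 = 61.9%; 52/87 = 59.8%.

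The smallest r that takes retention below 60% is the first integer above C/0.6 − 80:

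| C | C/80 | C/0.6 − 80 | smallest r |
|---|---|---|---|
| 48 | 60.0% | 0 | 1 |
| 50 | 62.5% | 3.3 | 4 |
| 52 | 65.0% | 6.7 | 7 |
| 54 | 67.5% | 10 | 11 |
| 56 | 70.0% | 13.3 | 14 |

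The effect shrinks if replaced patients complete T2. With C = 48 and r = 4, k = 1, 2 and 3 give 49/84 = 58.3%, 50/84 = 59.5% and 51/84 = 60.7%. With C = 52 and r = 7, k = 1 gives 53/87 = 60.9%.

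**Between-arm outcomes.** If all 4 replacements fall in the mPal arm, retention there goes from 24/40 = 60.0% to 24/44 = 54.5% (k = 0). An illustrative mPal referral rate of 12/40 = 30.0% becomes 12/44 = 27.3% if none of the 4 is referred, or 13/44 = 29.5% if one is. The t-test of change in Section 10.4.3 is affected only if replaced patients have T2 data.

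**The case against.** The strongest reply is that Section 8.2 is a recruitment rule. It says who may be replaced, not who leaves the analysis. The 40/40 in Section 10.3 can be read as the planned size, and because the objectives speak of enrolling and then retaining patients, the natural retention denominator is everyone enrolled. The protocol also works to keep patients in: Section 8.1 continues assessments, Section 8.3 has staff reschedule a missed intervention, and Section 9.1 repeats baseline items for late viewers. This is a reasonable reading, and it shows that exclusion is not stated. It does not remove the gap, because no section states that denominator, and following the replacement rule to fill 40/40 gives the other result.

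The effect is also small against the trial's precision. The exact 95% intervals for 48/80 (48.4% to 70.8%) and 48/84 (45.9% to 67.9%) overlap almost entirely. Section 10.4.2 names its binomial test for enrolment, and no go/no-go rule is attached to retention. This stands and limits the severity.

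A reader might infer three stronger points that the documents do not support:
- That every usual-care patient is replaceable because none receives mPal. The wording is most sensibly read as concerning patients due to receive the intervention; Section 7.1 gives the other arm usual care by design.
- That non-compliance withdrawals are a further route to replacement. Once a patient has received mPal, the second sentence of Section 8.2 rules replacement out.
- That patients found ineligible after assignment (Section 5.5) must be counted as not retained. Enrolment is defined among eligible patients, so leaving them out of retention is defensible if they are reported.

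**Conclusion.** The point holds as a gap that permits bias, not as a stated exclusion. Section 8.2, the 40/40 sample in Section 10.3 and the missing denominator in Section 10.4.2 together allow randomised mPal patients lost before viewing the tool to be swapped out.

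The 2.9-point illustration rests on three assumptions: 4 patients are replaced, they leave the denominator, and none completes T2. The 60% target is sensitive only when retention lies near it; at 70.0% observed, 14 replacements would be needed to bring it below target.

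A reader might infer that the primary result is compromised. It is not, if all approached and enrolled patients are counted. Retention is a secondary feasibility measure in a pilot, and effectiveness outcomes carry no formal hypotheses (Section 4.2). Severity is minor.

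**What to change.** - **Section 8.2:** limit replacement to patients not yet randomised, or keep the rule and state that replacements are additional patients who do not displace those already randomised.
- **Sections 10.3 and 10.4.2:** state that all eligible randomised patients, including those replaced or withdrawn, stay in the retention denominator and are analysed in their assigned arm. Use EHR referral data as far as each patient's consent allows, and change scores for those with T2 data.
- **Reporting:** give the numbers of replaced patients and of patients found ineligible after randomisation (Section 5.5), by arm.

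The cost is mainly wording, plus EHR extraction for replaced patients where consent permits. Reported retention may be slightly lower, and the number randomised may exceed 80 if replacements are added.
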